2 PURPOSE OF THE ANALYSES

The purpose of this statistical analysis plan (SAP) is to provide detailed information to aid in the implementation of the statistical analysis of the study data. It briefly summarizes the protocol, describes the analysis sets that will be analyzed, and describes the analyses to be performed. The details of the specific statistical methods that will be used are provided. Table, figure, and listing specifications are in separate documents. This analysis plan is meant to supplement the study protocol. If differences occur between analyses described in the SAP and the current protocol, those found in this SAP will assume primacy.

This SAP is written with due consideration of the recommendations outlined in the most recent International Conference on Harmonisation (ICH) E9 Guideline entitled Guidance for Industry: Statistical Principles for Clinical Trials and the most recent ICH E3 Guideline, entitled Guidance for Industry: Structure and Content of Clinical Study Reports and will be finalized prior to database lock.

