4 GENERAL ANALYSIS AND REPORTING CONVENTIONS

The following general analysis and reporting conventions will be used:

- Categorical variables will be summarized using counts (n) and percentages (%) and will be presented in the form n (%). If a count is 0, no percentage will be shown. To ensure completeness, summaries for categorical variables will include all categories, even if no subjects had a response in a particular category. Denominators will include subjects with non-missing data, unless otherwise specified. The number of subjects with missing data for categorical variables will be summarized without a percentage.
- Continuous variables will be summarized using mean, standard deviation (SD), minimum, maximum, median, and number of subjects. The mean, median, and confidence intervals (CI) will be rounded and reported to 1 more level of precision than the original observations, and the SD will be rounded and reported to 2 more levels of precision than the original observations. The minimum and maximum will be the same precision as the original data.
- Following SAS default rules, the median will be reported as the rounded average of the two middle numbers if the dataset contains even numbers.
- P-values, if any are provided, will be rounded and reported to 3 decimal places if greater than 0.001. If the rounded p-value is less than 0.001, '<0.001' will be reported. If the rounded p-value is >0.999, '>0.999' will be reported.
- Unless otherwise specified, the baseline value for all measures is the last non-missing value prior to the first dose, obtained on or before the date of the first dose of study drug. For measurements that occur on the date of the first dose of study drug with time collected, the measurement will be considered the baseline value if the measurement time is prior to the time of the first dose.
- No preliminary rounding will be performed; rounding will only occur after analysis. To round, consider digit to right of last significant digit: if < 5 then round down, if ≥ 5 then round up.
- All listings will be sorted in order of subject, parameter (when applicable), and time of assessment (e.g., visit, time, and/or event).
- Dates in listings will be displayed as yyyy-mm-dd (e.g., 2021-10-14).
- Age (in years) will be calculated as [(date of informed consent date of birth)] /365.25 and will be reported as the integer part of the derived age, with no rounding, in the analysis datasets, tables, and listings.

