8.2 Primary Endpoint

The repeatability of organ-specific quantitation of radiotracer uptake will be assessed using PET/CT imaging of ¹²⁴I-AT-01 in subjects with AL or ATTR systemic amyloidosis and will be presented using multiple methods by organ (heart, liver, spleen, and kidney) to explain the relationship and describe the variability between assessments. The quantitative methods that will be used are (1) repeatability coefficients, (2) Bland-Altman plots, (3) Intraclass Correlation Coefficients (ICC), and (4) Signal-to-Noise Ratio and Contrast-to-Noise Ratio vs SUV-based metrics plots. There are 3 readers at each time point and 2 reads per scan per reader for quantitative reads. The above quantitative methods will be deployed to measure multiple types of repeatability.

These methods are described in more detail in sections 8.2.1, 8.2.2, 8.2.3, and 8.2.4.

The SUV-based metrics are peak SUV (denoted SUVpeak, collected as suv_peak_organ from the imaging dataset), and max SUV (denoted SUVmax, collected as suv_max_organ from the imaging dataset).

In addition to the above quantitative methods, AT-01 uptake will be visually determined by three expert radiologists for each scan of each organ. Agreement among the three reads will be evaluated by scan using Fleiss' kappa. Agreement between each reader's two scans will be evaluated using Cohen's kappa. Details are described in section 8.2.5.

The quality of imaging results will be taken into consideration such that any images with a "Not Readable" indication of scan image quality will be excluded from primary analyses.

All imaging results will be listed.

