8.2.1 Repeatability Coefficient

8.2.1.1 Repeatability coefficients using observed values

• Computation of the Endpoint

The repeatability coefficient is the value under which the difference between any two repeat measurements of the same measurand acquired under repeatability conditions should fall within 95% probability.

If we assume normality of the repeated measurements, we have:

Repeatability Coefficient = 1.96
$$\times \sqrt{\frac{\sum (m_2 - m_1)^2}{n}}$$

Page 17 of 38

Version Date: 2022-12-16 Version: 2.0

Statistical Analysis Plan – AT01-001

where m_1 and m_2 are the two measurements performed on each of the n subjects.

• Analysis of the Endpoint

Summary tables with the repeatability coefficients for SUVpeak and SUVmax by organ will be produced 2 different ways:

- 1. Within Reader by Reader and Visit: where m₁ and m₂ are the 2 reads for a specific reader and visit.
- 2. Between Visit by Reader: where m₁ is the average of the 2 reads for a specific reader at Visit 1 and m₂ is the average of the 2 reads for the same reader at Visit 2.

8.2.1.2 Repeatability coefficients and within-subject coefficient of variation using log-transformed data

• Computation of the Endpoint

For the following calculations, $d_{ln} = \ln(m_2) - \ln(m_1)$ and m_1 and m_2 are the two measurements performed on each of the n subjects:

The repeatability coefficient is estimated as RC = $(\exp(\pm 1.96\text{SD}(d_{ln}))-1) \times 100$.

The within-subject coefficient of variation is wCV% = $(\exp(SD_{d \ln}/\sqrt{2}))-1) \times 100$.

• Analysis of the Endpoint

A summary table with the 95% repeatability coefficient and within-subject coefficient of variation for SUVpeak and SUVmax by organ will summarize repeatability in 2 different ways:

- 1. Within Reader by Reader and Visit: where m₁ and m₂ are the 2 reads for a specific reader and visit.
- 2. Between Visit by Reader: where m₁ is the average of the 2 reads for a specific reader at Visit 1 and m₂ is the average of the 2 reads for the same reader at Visit 2.

In addition to the above statistics, descriptive statistics of the average of and difference of m_1 and m_2 will be presented.

All of these analyses will be conducted on the image evaluable population for subjects with organs/visits where positive AT-01 uptake is detected by all three expert radiologists.

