8.2.2 Bland-Altman Plots

• Computation of the Endpoint

Document Control No.: TMP-SA-008-01

Each of the n subjects will be represented on the graph by assigning the mean of two measurements as the x-value and the difference between the two measurements as the y-value:

$$\left(\frac{m_1+m_2}{2},m_2-m_1\right)$$

Page 18 of 38

Version Date: 2022-12-16 Version: 2.0

Template Effective Date: 23 Mar 2021

where m_1 is the first measurement and m_2 is the second measurement taken for each of the n subjects. The x-axis will be labeled "Average of the two measurements" and the y-axis will be labeled "Difference between two measurements". A horizontal solid line will be plotted at the mean difference between the values (i.e. $y = \bar{x}$). Horizontal dashed lines will be plotted

at the limits of agreement given by: $= \bar{x} \pm 1.96 \times \sqrt{\frac{\sum ((m_2 - m_1) - \bar{x})^2}{n}}$, where $\bar{x} = \frac{\sum (m_2 - m_1)}{n}$.

The values of all 3 horizontal lines will be displayed on each plot.

• Analysis of the Endpoint

Plots will be produced for SUVpeak and SUVmax by organ for the Image Evaluable Set in 2 different ways:

- 1. Between Reader by Visit: where m_1 is the average of the 2 reads for a specific reader and visit and m_2 is the average of the 2 reads for a different reader for the same visit.
- 2. Between Visit by Reader: where m₁ is the average of the 2 reads for a specific reader at Visit 1 and m₂ is the average of the 2 reads for the same reader at Visit 2.

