8.2.5 Inter-rater and Intra-rater Agreement

AT-01 uptake is determined by three expert radiologists determination of AT-01 uptake for each region, it is one evaluation per expert per organ per visit. The number and % of subjects with positive AT-01 uptake will be described by expert by visit and organ. The inter-rater agreement in positive AT-01 uptake between the three expert radiologist's determination by visit will be presented using Fleiss' kappa. The intra-rater agreement in positive AT-01 uptake between Scan 1 and Scan 2 in each expert radiologist's determination by expert will be presented using Cohen's kappa and its 95% confidence interval.

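### SAP 8.2.2 divides by n around an estimated mean, so its limits of agreement are too narrow; and no unfiltered log-scale between-visit RC or wCV stands beside the one restricted to unanimous positive calls

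*SAP*

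**What the plan says.** **Limits of agreement (SAP 8.2.2).** "Plots will be produced for SUVpeak and SUVmax by organ for the Image Evaluable Set", between readers and between visits. The mean difference is a solid line. "Horizontal dashed lines will be plotted" at that mean plus or minus 1.96 times the root of the sum of squared deviations from it, divided by n. The values of all three lines are printed on each plot. No uptake restriction is stated.

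**Repeatability (SAP 8.2.1).** The log-scale RC and wCV depend on the data only through SD(d_ln), the SD of the difference in log SUV. A between-visit pair is one reader's mean of two reads at Visit 1 and the same reader's mean at Visit 2. The closing sentence of 8.2.1.2 limits the analyses to the image evaluable population "for subjects with organs/visits where positive AT-01 uptake is detected by all three expert radiologists". Under SAP 8.2.5, for the visual call, "it is one evaluation per expert per organ per visit", so an organ can be unanimous at one visit and not at the other. Neither document says how a pair that spans two visits qualifies, or whether the sentence also governs 8.2.1.1. It may be settled elsewhere, because "Table, figure, and listing specifications are in separate documents" (SAP 2).

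**Other planned output.** SAP 8.2.1.2 adds that "descriptive statistics of the average of and difference of m_1 and m_2 will be presented". SAP 4 says "Continuous variables will be summarized using mean, standard deviation (SD), minimum, maximum, median, and number of subjects". SAP 8.2 says "All imaging results will be listed".

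**The concern.** An SD taken around a mean estimated from the same n values has n-1 degrees of freedom. Dividing by n biases it low, and the bias grows as n falls. The study has up to 20 subjects, is analysed by organ, and is repeated for AL and ATTR (SAP 8.3), so plots with 5 to 10 points are realistic. The n divisor in the observed-value RC of 8.2.1.1 is not at fault, because that formula does not subtract a mean. SAP 8.2.6 itself uses n-1 for a coefficient of variation around an estimated mean.

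The second matter is selection. If both visits must be unanimous, an organ near the visual threshold whose repeat scan happens to read low is dropped. That pair would have contributed a large difference. The log-scale between-visit figures are the study's percentage measure of test-retest noise, and that noise bears on whether the tracer can be used to monitor progression and response. The plan gives no log-scale result without the filter, so a reader could not see how much the filter changes it.

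**Working it through.** The documents give no SUV variability, positivity rate, RC or wCV, so there is no stated figure to reproduce.

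**1. Limits of agreement**

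Ratio of the written half-width to the n-1 half-width: sqrt((n-1)/n).

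For normal differences, a new difference minus the estimated mean has SD sigma x sqrt(1+1/n). Expected coverage is therefore 2 x T(c) - 1, where T is the t distribution function on n-1 degrees of freedom:
- with n-1: c = 1.96 / sqrt(1+1/n)
- as written: c = 1.96 x sqrt((n-1)/(n+1))

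| n | ratio | too narrow by | coverage as written | coverage with n-1 |
|---|---|---|---|---|
| 20 | 0.975 | 2.5% | 92.2% | 92.9% |
| 10 | 0.949 | 5.1% | 89.0% | 90.6% |
| 5 | 0.894 | 10.6% | 81.5% | 85.2% |

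**2. Selection on unanimous calls**

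All inputs here are assumptions. Log SUV at each visit is an organ effect (SD 0.6) plus visit error (SD 0.10, 0.25 or 0.35). Each of three readers calls positive if that value plus reader noise (SD 0.10) exceeds a threshold that makes 30%, 50%, 70% or 90% of reads positive. There are 2 million pairs per setting. SD(d_ln) with both visits unanimous is compared with SD(d_ln) for all pairs:

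- Constant relative error: ratio 0.80 to 0.99, so 1-20% smaller.
- Relative error rising with uptake (error SD times exp(0.3 x organ effect)): 0.97 to 1.18, so the direction can reverse.
- Relative error falling with uptake (exp(-0.3 x organ effect)): 0.61 to 0.92.
- Calls unrelated to scan error: 1.00.

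The central case has 50% positive and visit SD 0.25. Without a filter, SD(d_ln) = 0.25 x sqrt(2) = 0.354. The SAP formulas then give:
- wCV = exp(0.354/sqrt(2)) - 1 = 28.4%
- RC = exp(±1.96 x 0.354) - 1 = -50%/+100%

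With both visits unanimous the ratio is 0.889, so SD(d_ln) = 0.314, wCV is 24.9% and RC is -46%/+85%. About 20% of organs unanimous at Visit 1 drop out at Visit 2.

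A second set of assumptions (organ SD 0.3 to 0.6, visit SD 0.10 to 0.30, 30-90% positive) gave 0.99 down to 0.69. The low end arises when visit error is as large as the spread between organs. Selecting pairs that are unanimous at either visit gave 1.01 to 1.19, an overstatement.

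**3. What the planned output already gives**

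Let xbar be the printed mean difference and h the printed half-width as now defined. Because both formulas divide by n, the unfiltered observed-value RC is exactly sqrt(h² + (1.96 x xbar)²). Once 8.2.2 uses n-1, it becomes sqrt(h² x (n-1)/n + (1.96 x xbar)²).

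The number of dropped pairs is the within-reader n at Visit 1 minus the between-visit n, if no reads are missing. No comparable route leads from the planned tables and plots to the unfiltered log-scale RC or wCV.

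**4. Sampling error for comparison**

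The 95% interval for an SD, sqrt((n-1)/chi-square quantile), runs from 0.76 to 1.46 times the estimate at n=20 and from 0.69 to 1.83 at n=10.

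**The case against.** Repeatability in organs with visible uptake is a defensible target, and the unfiltered set adds organs of a different kind. That stands, and it is why the restricted analysis should remain.

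The text also has a natural reading: each organ-visit must be unanimous, so a pair needs both. A reader might infer that the wording leaves programmers no guidance. The documents do not support that; a clarifying clause is enough.

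A reader might infer that the reported RC and wCV will be too small. The documents do not establish this. They give no uptake distribution and no link between calls and measured uptake. If positive and negative organs separate clearly, few lie near the threshold. With 50% positive, visit SD 0.25 and group means 1.2, 1.6 or 2.0 log units apart, SD(d_ln) with both visits unanimous is 0.95, 0.97 or 0.99 times that with Visit 1 selection alone. The likely bias is smaller than the sampling error, and no acceptance limit depends on it.

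A reader might also infer that pairs should be selected on Visit 1 alone. That has its own artefact. With no true change it shifts the mean log difference by -0.004 to -0.22 (central -0.085) through regression to the mean, and the SD-based formulas ignore that shift.

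On the divisor, most of the shortfall from 95% coverage comes from using 1.96 with few subjects. At n=20 that accounts for 2.1 points (95 - 92.9) and the divisor for 0.7 (92.9 - 92.2). At n=5 they are 9.8 and 3.7. This is true, but the divisor is still wrong and costs nothing to correct.

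**Conclusion.** The divisor in SAP 8.2.2 is wrong as written. The narrowing of 2.5%, 5.1% and 10.6% at n=20, 10 and 5 is exact and needs no assumption about the data. The coverage figures assume normal differences.

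The selection point holds conditionally. With both visits required, calls that track the repeat scan's uptake, and roughly constant relative error, SD(d_ln) falls by about 1-20% against no filter under the main assumptions. The size cannot be fixed from the documents, and the effect may be absent or reversed. It does not show the primary analysis to be invalid. It supports one cheap comparison that the plan lacks. No direction is claimed for the observed-value RC, whose unfiltered version is already recoverable.

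**What to change.** 1. In SAP 8.2.2, replace n by n-1 in the limits of agreement. Leave the divisor in 8.2.1.1 as it is.
2. In SAP 8.2.1, state that a between-visit pair requires unanimous positive calls at both visits, and say whether the restriction also covers 8.2.1.1. Keep this as the restricted analysis.
3. Beside it, report the between-visit log-scale RC and wCV on all Image Evaluable organs, with the number of pairs in each column.

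An entry in SAP 12 noting the restriction is optional: protocol 9.4 does not mention it, but the protocol leaves methodology to the SAP.

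The cost is a few words, one changed divisor and one extra column. No new data are needed. The limits will be slightly wider, and the unfiltered percent RC may look slightly less favourable.

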8.2.2 Bland-Altman Plots

• Computation of the Endpoint

Document Control No.: TMP-SA-008-01

Each of the n subjects will be represented on the graph by assigning the mean of two measurements as the x-value and the difference between the two measurements as the y-value:

$$\left(\frac{m_1+m_2}{2},m_2-m_1\right)$$

Page 18 of 38

Version Date: 2022-12-16 Version: 2.0

Template Effective Date: 23 Mar 2021

where m_1 is the first measurement and m_2 is the second measurement taken for each of the n subjects. The x-axis will be labeled "Average of the two measurements" and the y-axis will be labeled "Difference between two measurements". A horizontal solid line will be plotted at the mean difference between the values (i.e. $y = \bar{x}$). Horizontal dashed lines will be plotted

at the limits of agreement given by: $= \bar{x} \pm 1.96 \times \sqrt{\frac{\sum ((m_2 - m_1) - \bar{x})^2}{n}}$, where $\bar{x} = \frac{\sum (m_2 - m_1)}{n}$.

The values of all 3 horizontal lines will be displayed on each plot.

• Analysis of the Endpoint

Plots will be produced for SUVpeak and SUVmax by organ for the Image Evaluable Set in 2 different ways:

- 1. Between Reader by Visit: where m_1 is the average of the 2 reads for a specific reader and visit and m_2 is the average of the 2 reads for a different reader for the same visit.
- 2. Between Visit by Reader: where m₁ is the average of the 2 reads for a specific reader at Visit 1 and m₂ is the average of the 2 reads for the same reader at Visit 2.

8.2.3 Intraclass Correlation Coefficient (ICC)

• Computation of the Endpoint

A two-way mixed effects model with absolute agreement type for a single rater/measurement will be used to calculate the intraclass correlation coefficient. SAS Proc Mixed with subject as a random effect will be used to produce covariance parameter estimates.

ICC will be calculated as the covariance parameter estimate for subject divided by the sum of the covariance parameter estimates for subject and residuals.

Fisher's z-transformation will be used to calculate a 95% CI of ICC (r) where

$$z' = \frac{1}{2} \ln \frac{1+r}{1-r}$$
, and $SE_{z'} = \frac{1}{\sqrt{N-3}}$, making the 95% CI = $z' \pm 1.96$ SE_{z'}

To transform the endpoints of the CI back to correlation coefficients, the following formula will be used: $=\frac{\exp(2z)-1}{\exp(2z)+1}$.

• Analysis of the Endpoint

A summary table with the ICC for SUVpeak and SUVmax by organ will be produced "Among Reader by Visit": where m_1 is the average of the 2 reads for a specific reader and visit, m_2 is the average of the 2 reads for the second reader and m_3 is the average of the 2 reads for the third reader for the same visit.

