9.5.1 General Considerations

This is an open-label, single arm study. In general, for continuous variables, the mean, standard deviation (SD), median, and range will be presented. Categorical variables will be summarized by frequency counts and percentages.

Subject disposition will be summarized for all subjects who signed the ICF and will include the number of subjects who received study treatment and the number and percentage of subjects who completed or prematurely discontinued the study, classified by reasons for premature discontinuation.

Discontinuations

The reason for study discontinuation and the number of days post-study drug treatment on which the subject discontinued will be summarized.

Protocol Deviations

Protocol deviations will be provided in a listing with reasons for the deviation and the date of occurrence. Any exclusion of subjects from exploratory analysis populations, and how these exclusions impact data analysis, will be addressed in the clinical study report.

Missing Data

There will be no imputation for missing safety or whole blood radioactivity data.

9.5.2 **Primary Endpoint(s)**

The primary objective of this study is to evaluate the repeatability of organ-specific quantitation of radiotracer uptake following PET/CT imaging of AT-01 in subjects with AL or ATTR systemic amyloidosis. The corresponding primary endpoint is:

 Repeatability coefficient (Bland-Altman plots) and intraclass correlation coefficient (ICC) associated with the quantification of radioactivity associated with organ level ¹²⁴I-AT-01 uptake measurements.

The signal to noise ratio (SNR) and contrast to noise ratio (CNR) will be plotted against standardized uptake value (SUV) based metrics. Repeatability will be assessed using Bland-Altman plots. ICC and its associated 95% confidence interval will be presented. Quantitative organ uptake analyzed by an automated method will be summarized. Between-reader agreement in visual determination of AT-01 uptake will be evaluated by Cohen's kappa.

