8.3 Examination of Subgroups

The repeatability coefficients, Bland-Altman plots, and intraclass correlation coefficients described in section 8.2 will be repeated by amyloid type: (AL versus ATTR).

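### SAP 8.2.3 names a two-way absolute-agreement ICC but gives a formula with no reader term, and its 95% CI uses the standard error of a Pearson correlation of pairs

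*SAP*

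**What the plan says.** SAP 8.2.3 specifies the ICC in four steps.

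- **Type.** "A two-way mixed effects model with absolute agreement type for a single rater/measurement will be used to calculate the intraclass correlation coefficient".
- **Model.** "SAS Proc Mixed with subject as a random effect will be used to produce covariance parameter estimates". No reader effect, fixed or random, is mentioned.
- **Estimator.** "ICC will be calculated as the covariance parameter estimate for subject divided by the sum of the covariance parameter estimates for subject and residuals".
- **Interval.** Fisher's "z-transformation will be used to calculate a 95% CI of ICC (r) where" z' = 0.5 ln((1+r)/(1-r)) and its standard error is 1/sqrt(N-3). N is not defined.

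Each ICC is calculated among readers within a visit, by organ and SUV metric. SAP 8.2 states that "There are 3 readers at each time point and 2 reads per scan per reader for quantitative reads". The two reads are averaged, so each subject contributes three values; "m_3 is the average of the 2 reads for the third reader for the same visit".

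The ICC is part of the primary endpoint. Protocol 9.5.2 commits to the interval: "ICC and its associated 95% confidence interval will be presented". Under SAP 8.3 the "intraclass correlation coefficients described in section 8.2 will be repeated by amyloid type: (AL versus ATTR").

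**The concern.** The label and the calculation do not match, and the text does not show which one governs. An absolute-agreement ICC carries the reader variance in its denominator, and the SAP's ratio has no such term. There are two ways to carry out the instructions:

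- **Reader left out.** Reader differences fall into the residual. The ratio is the one-way ICC, which still penalises disagreement between readers.
- **Reader fitted as fixed**, as the two-way mixed label suggests. The reader means are removed before the residual is estimated. The ratio is then a consistency ICC that ignores systematic reader differences.

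Two competent programmers could therefore report different values from the same data, both labelled absolute agreement. The SAP takes precedence over the protocol where they differ (SAP section 2), so the protocol cannot settle it.

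The interval is a separate fault. The standard error 1/sqrt(N-3) is the large-sample result for a correlation of N pairs. It does not depend on the number of readings per subject, which here is three. This is the only confidence interval planned for the quantitative primary endpoint. SAP 8.2.1 and 8.2.2 plan none for the repeatability coefficients or limits of agreement, and the kappa interval in 8.2.5 concerns visual reads.

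**Working it through.** The documents give no expected ICC, variance components or subject numbers by organ or amyloid type, so there is no planned figure to reproduce. From the documents: three values per subject (k = 3), up to 20 subjects, multiplier 1.96. Assumed: ICC 0.90 for illustration, 12 and 8 subjects for smaller organ or subgroup sets, and the variance components below. N is read as subjects, because SAP 8.2.1 and 8.2.2 count subjects.

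**1. Which ICC the formula gives.** One simulated data set (20 subjects, three readers, large reader shifts) was fitted by REML. Without reader, the SAP ratio was 0.362, equal to the ANOVA one-way ICC. With reader fixed it was 0.744, equal to the consistency ICC. The absolute-agreement ICC was 0.447, so neither fit gives the ICC named.

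**2. Interval at r = 0.90, 20 subjects.**

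- SAP: z' = 0.5 ln(1.9/0.1) = 1.472; half-width 1.96/sqrt(17) = 0.475; back-transformed limits 0.760 to 0.960.
- Exact one-way F: F = (1 + 2 x 0.9)/(1 - 0.9) = 28 on n-1 = 19 and 2n = 40 df. Lower F = 28/2.086 = 13.42, upper F = 28 x 2.333 = 65.32. Limits (F-1)/(F+2): 0.805 to 0.955.

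| Subjects | SAP interval | Exact one-way F | SAP excess width |
|---|---|---|---|
| 20 | 0.760 to 0.960 | 0.805 to 0.955 | 33% |
| 12 | 0.674 to 0.972 | 0.766 to 0.967 | 48% |
| 8 | 0.534 to 0.982 | 0.720 to 0.977 | 74% |

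On the z' scale at 20 subjects the SAP standard error is 1/sqrt(17) = 0.2425. The delta-method value for three readings is sqrt(2/(3 x 2 x 19)) x 2.8/1.9 = 0.195, so the SAP value is about 24% too large. If N were read as 60 readings, it would be 1/sqrt(57) = 0.1325, about 32% too small, and the interval would be 0.837 to 0.939.

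**3. Coverage with no reader differences, true ICC 0.90** (20,000 simulated data sets per setting). With N as subjects and reader omitted, the SAP interval covers 98.3% at 20 subjects (mean width 0.214, against 0.160 for the F interval) and 98.8% at 8 (0.507 against 0.299). The F interval covers 95.1% and 95.0%. With N as 60 readings, coverage falls to about 82%.

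**4. With reader differences.** Between-subject variance 1, residual variance 0.05, reader offsets -d, 0, +d, so the reader variance is d squared. At d = 0.3 the true absolute-agreement ICC is 1/(1 + 0.09 + 0.05) = 0.877. At 20 subjects:

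| Calculation | Median ICC | SAP interval coverage of 0.877 |
|---|---|---|
| Reader omitted | 0.870 | 98.7% |
| Reader fixed | 0.952 | 48% |
| Absolute-agreement ICC | 0.874 | not applicable |

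With reader fixed, coverage of the true value is 84% at d = 0.2 and 97% at d = 0.1. At d = 0.3 it is 75% with 12 subjects and 89% with 8, because the interval widens.

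**The case against.** The strongest reply is that the operative sentences in 8.2.3 never mention a fixed reader effect. Followed literally, they give the one-way ICC, whose median of 0.870 is very close to 0.874 for the absolute-agreement ICC. The interval then errs on the cautious side, and at 20 subjects the lower limit moves only from 0.805 to 0.760.

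The 48% coverage needs both a programmer who adds the fixed term and a reader variance nearly twice the residual variance. With the same offsets and a residual variance of 0.30, fixed-reader coverage is about 97% and the medians are 0.768 (fixed), 0.711 (omitted) and 0.717 (absolute agreement). The 12- and 8-subject figures also rest on assumed set sizes.

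Little hangs on the result. The study has no hypothesis and no ICC threshold. The visit-to-visit objective is carried by the between-visit repeatability coefficients and plots. Reader offsets still appear in the between-reader Bland-Altman plots and enter the six-measurement coefficient of variation in SAP 8.2.6.

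These points stand as limits on the size of the problem. They do not remove it. The label invites the fixed term, nothing in the SAP excludes it, and the interval is wrong for three readings whichever model is fitted. An undefined N also leaves open a reading that makes the interval too narrow.

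**Conclusion.** The concern holds. SAP 8.2.3 names one ICC and computes another, and its interval does not suit the data.

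On the literal reading, with reader omitted and N as subjects, the point estimate is close to absolute agreement and the interval is too wide: by a third at 20 subjects and by about three quarters at 8, at an ICC of 0.90. With reader fixed, the ICC can be overstated and the interval can miss the absolute-agreement value; how badly depends on reader differences that the documents do not quantify, so the 48% is a conditional case.

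The effect is confined to the among-reader, within-visit ICC and its amyloid-type repeats. Repeatability coefficients and Bland-Altman limits are untouched. It should be corrected because it concerns a primary-endpoint statistic, but it changes no test decision.

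**What to change.** Amend SAP 8.2.3 as follows.

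1. **Model and estimator.** Write out the Proc Mixed model with reader included. Compute Vsubject/(Vsubject + Vreader + Vresidual). Proc Mixed supplies a reader variance only if reader is random. If readers are to stay fixed, compute the absolute-agreement ICC from the two-way ANOVA mean squares: (MSsubject - MSerror)/(MSsubject + 2 MSerror + (3/n)(MSreader - MSerror)). State which route is used.
2. **N.** Define it as the number of subjects contributing to that organ, metric and visit.
3. **Interval.** Replace the Fisher interval with one derived for an ICC. Of those tested, the exact one-way F interval (between- and within-subject mean squares, n-1 and 2n df) did best: 94.6% to 96.8% coverage of the absolute-agreement ICC over 8, 12 and 20 subjects and offsets from 0 to 0.3. If the conclusion is meant to extend beyond these three readers, use the F-based absolute-agreement interval and say so.

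The cost is wording and a few lines of code, with no extra data. If readers differ, the ICC will be lower than a fixed-reader fit would show. The one-way F interval is exact only without reader offsets and is slightly conservative with them. The F-based absolute-agreement interval treats readers as random and can be wider than the SAP interval: mean width 0.49 against 0.26 for the reader-omitted version, at 20 subjects and d = 0.3. A plain percentile bootstrap over subjects is best avoided at this size; it covered 80% to 83% at 8 subjects and 89% to 92% at 20.
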